Both HVPG and HQ-SHUNT results correlate with fibrosis stage, prevalence of cirrhosis, and the prevalence and size of varices [7], [8], [9]. DSI appears to have a better and more linear correlation with fibrosis, and more sensitivity at lower fibrosis stages than HVPG (Fig. 3). However all the results summarized above were from separate studies and the two methods have never before been compared in a head-to-head fashion.

IV. Research Methods

A. Outcome Measure(s):

The following outcome measures will be assessed for each Specific Aim:

Primary Aim 1. Two measurements will be compared, HVPG and DSI. The HVPG test results will define the patients with portal hypertension (HVPG ≥ 6 mmHg). DSI will be determined from the HepQuant (HQ)-SHUNT test and the DSI cutoff for portal hypertension will be defined from ROC analysis.

Primary Aim 2. Two measurements will be compared, HVPG and DSI. The relationship between these measurements, in the patients with portal hypertension, will be analyzed by linear and nonlinear regression.

Exploratory Aims:

Exploratory Aim 1. The outcome measure is cirrhotic fibrosis score on liver biopsy. Prevalence of cirrhosis will be determined for cutoffs of DSI 20 and HVPG 6 mmHg.

Exploratory Aim 2. The outcome measure is medium to large varices at EGD. Prevalence of varices will be determined for cutoffs of DSI 20 and HVPG 10 mmHg.

Exploratory Aim 3. The outcome measure is patient tolerability for testing procedures defined by the Patient Survey.

B. Description of Population to be Enrolled:

Inclusion Criteria

- Liver disease patient scheduled to have an Hepatic Venous Pressure Gradient (HVPG) procedure
- At time of enrollment, being between the ages of 18 and 75

Exclusion Criteria

- Concomitant treatment with both a beta blocker and an ACE inhibitor
- Concurrent hepatic malignancy. Patients with a history of treated HCC can be included if there is no evidence of recurrent disease at the time of this study.
- Unstable angina or history of myocardial infarction or congestive heart failure within 6 months prior to enrollment into this study
- Renal insufficiency with chronic kidney disease stage 4 or 5 (GFR < 30 mL/min/1.73m²)
- Crohn's disease or any active intestinal inflammatory condition
- Having had an ileal resection
- Diabetic Gastroparesis
- Pregnancy or intent to become pregnant. Urine pregnancy tests will be performed prior to HQ SHUNT testing.
- Inability to consent for one's self

Stopping Criteria

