- Decision by subject to withdraw from study for any reason
- Development of any of the above-mentioned exclusion criteria (being diagnosed with a hepatic malignancy, becoming or intending to become pregnant, clinical decompensation, development of unstable coronary disease, congestive heart failure or renal insufficiency with GFR < 30mL/min/1.73m²)
- Adverse reaction to test compounds

C. Study Design and Research Methods

Patient Selection

The HVPG procedure costs ~\$8500 and is currently ordered on a case-by-case basis as part of the standard of care (SOC) for liver disease. Patients already scheduled to have an HVPG measurement will be recruited to participate in this study of "Correlation and Comparison of HQ-SHUNT with HVPG". The HVPG procedure is quite uncomfortable, requires sedation and commitment of an entire day. Therefore, patients will not undergo HQ-SHUNT testing on the day of their HVPG, but rather within a window of ±60 days of their HVPG. Liver disease progresses slowly over years so that HQ-SHUNT® and HVPG results will represent the patient's current status. Patients will be censored in the analysis if clinical decompensation occurs between the HQ-SHUNT and HVPG tests.

We will enroll 110 patients into the study. Over 90% of all HVPG tests performed by UCH Radiology are ordered through the Hepatology clinic at UCH. Patients and care providers in the Hepatology clinic will be made aware of the "Correlation and Comparison of HQ-SHUNT with HVPG" study via direct communications. Patients may be enrolled within 60days following the performance of the HVPG procedure. HQ-SHUNT tests will only be performed in the patients who had a technically successful HVPG test as determined by the radiologist performing the procedure. All HQ-SHUNT tests will be performed within the 60 days following the HVPG test. HQ-SHUNT will only be performed in patients whose clinical status is stable and who have not had any major intervening procedures such TIPS or surgical shunt. Elective EGD and banding of varices, in an otherwise clinically stable patient is an allowable intervention.

PROCEDURES AND METHODS

HVPG

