We do not believe the effects of the oral or intravenous cholate are harmful to a fetus, however the effects are not definitively known. Because of this, we will not enroll participants into this study who are or are planning to become pregnant. We recommend using a reliable form of birth control throughout the study. Hormonal birth control pills, intrauterine device (IUD), DepoProvera, Norplant, barrier methods (condom or diaphragm) plus a spermicidal agent, surgical sterilization, and complete abstinence are examples of reliable methods of birth control. All women of child-bearing potential will be given a urine pregnancy test prior to HepQuant testing to ensure the subject is not pregnant.

Beta blockers or ACE inhibitors could affect the blood flow to the liver, so patients who are currently taking either a beta blocker or an ACE inhibitor will be asked to delay taking their normal dose on the morning of their test until their test is completed. Merely delaying the dose of a beta blockers or ACE inhibitor for a few hours would only minimally increase risk to subjects, similar to that of patients who miss doses of medications in everyday life. To minimize risk, patients taking both a beta blocker and an ACE inhibitor will be excluded. To further minimize risk, patients with a history of ongoing or unstable angina, or recent myocardial infarction, or congestive heart failure (within 6 months of enrollment) will also be excluded.

Placing the indwelling intravenous catheter for the HQ-SHUNT test will cause minor pain and discomfort. With any blood draw there is a small risk of hematoma and a very small risk of a blood clot (1 in 100) or infection (1 in 1000). As part of numerous COMIRB approved studies, on healthy controls and liver disease patients with HCV, PSC, and NASH, we have performed the HQ SHUNT test over 1000 times in over 500 individuals. Most subjects had the test multiple times. There has never been an adverse event so we believe the risk from the test is very small.

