Study data will be collected and managed using REDCap (Research Electronic Data Capture). REDCap is a secure, web application designed to support data capture for research studies, providing user-friendly web-based case report forms, real-time data entry validation (e.g. for data types and range checks), audit trails and a de-identified data export mechanism to common statistical packages (SPSS, SAS, Stata, R/S-Plus). The system was developed by a multi-institutional consortium which includes University of Colorado Denver and was initiated at Vanderbilt University. REDCap is HIPAA compliant and can be configured to be Part 11 compliant.

E. Potential Scientific Problems:

Concomitant medication use could theoretically present potential interference in serum cholate measurement. The liquid chromatography-mass spectrometry (LCMS) technique used to measure cholate levels was validated according to FDA guidelines [11] for selectivity, accuracy, precision, recovery, stability, and freedom from interferences by serum components or medications. Freedom from interference was tested on blanks and at the LLOQ for each analyte with a number of metabolites and medications including: Bilirubin, Cholesterol, Carbamazepine, Oxazepam, Diazepam, Nordiazepam, Lorazepam, Temazepam, Flunitrazepam, Nitrazepam, Clonazepam, Alprazolam, Ephedrine, Codeine, Diphenhydramine, Nortriptyline, Propoxyphene, d-Amphetamine, d-Methamphetamine, Phenylpropanolamine, Phenmetrazine, Caffeine, Phencyclidine, Imipramine, Spironolactone, Furosemide, and dl-Propranolol. There was no interference at the concentrations tested which were above those usually observed in patient serum samples.

The circulatory changes seen in medical conditions, including right and left-sided heart failure or severe renal failure, could affect IV and oral cholate clearances. Therefore, patients with ongoing heart failure or with GFR < 30 mL/min/1.73m² corresponding to chronic kidney disease stage 4 or 5 will be excluded.

F. Data Analysis Plan:

Power and Sample size

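### Section IV.D says that ongoing as well as unstable angina is excluded, to lower the risk of the dose delay, but the exclusion list bars only unstable angina

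*Combined protocol and SAP*

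**What the plan says.** Section IV.D (Description, Risks and Justification of Procedures and Data Collection Tools) notes that beta blockers and ACE inhibitors may alter hepatic blood flow. A patient on either class "will be asked to delay taking their normal dose on the morning of their test until their test is completed". The section rates the added risk of a delay of a few hours as minimal, then gives two exclusions that reduce it. The first covers patients taking both drug classes. The second, given as a way to lower risk further, names "patients with a history of ongoing or unstable angina, or recent myocardial infarction", as well as congestive heart failure, with a window of 6 months before enrollment, and states that these patients are excluded as well.

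The Exclusion Criteria in Section IV.B carry the first as "Concomitant treatment with both a beta blocker and an ACE inhibitor". Their cardiac entry is "Unstable angina or history of myocardial infarction or congestive heart failure within 6 months prior to enrollment into this study".

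The Stopping Criteria, in the same section, end participation when a patient develops one of the exclusion criteria. Their cardiac and renal terms are "development of unstable coronary disease, congestive heart failure or renal insufficiency".

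**The concern.** Section IV.D names two kinds of angina, ongoing and unstable, joined by *or*. The exclusion list names one. Someone screening from the list and someone screening from Section IV.D can reach opposite decisions on the same patient.

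The difference matters because of where the sentence stands. The study itself imposes the dose delay; it is not part of usual care. Section IV.D is where the protocol explains to an ethics committee why the delay is acceptable. A committee relying on that section would believe that patients with ongoing angina are never asked to delay a dose. The list does not ensure that. At stake is who is exposed to a study-imposed delay, and whether the stated risk justification describes the patients who can actually enroll.

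**Working it through.** No figure in the plan bears on this point, so the check sets the provisions side by side.

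| Term | IV.D risk justification | IV.B Exclusion Criteria | IV.B Stopping Criteria |
|---|---|---|---|
| Both drug classes together | Excluded | Excluded | Covered only by the general reference to the exclusion criteria |
| Unstable angina | Excluded | Excluded | Unstable coronary disease |
| Ongoing angina, not unstable | Excluded | Not listed | Not listed |
| Myocardial infarction | Excluded if recent | Excluded, 6 months | Covered only by the general reference |
| Congestive heart failure | Excluded, 6 months | Excluded, 6 months | Listed, no window |

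Only the third row differs in substance between Section IV.D and the exclusion list.

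Now follow one patient: ongoing angina that is not unstable, a beta blocker but no ACE inhibitor, and no other condition on the list.

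1. *Drug criterion.* The list bars only the combination ("Concomitant treatment with both a beta blocker and an ACE inhibitor"), so the patient passes.
2. *Cardiac criterion.* The list bars unstable angina, and infarction or heart failure within 6 months. None applies, so the patient passes.
3. *Stopping Criteria.* These concern developments after enrollment, and the coronary term is unstable disease. None applies.
4. *Dose delay.* The patient takes one of the two drug classes, so Section IV.D asks for the dose to be delayed.
5. *Section IV.D exclusion.* The same paragraph says that patients with ongoing angina are excluded, so this patient should not have reached step 4.

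Steps 1 to 4 and step 5 cannot both hold. The result is the same for a patient taking an ACE inhibitor alone.

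*Size.* The number exposed would be 110 (planned enrollment, Section IV.C) × the proportion with ongoing angina that is not unstable × the proportion of those taking exactly one of the two drug classes. The documents give neither proportion, so the product cannot be evaluated, and zero is possible.

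**The case against.** The strongest reply is that Section IV.D is part of the protocol and itself commits to excluding these patients. Nothing says that only the bulleted list is applied, and the HQ-SHUNT tests are done at one center. A reader who applies the whole document would exclude the patient. This stands as a limit on the consequence: wrongful enrollment is possible, not certain. It does not remove the contradiction, because the list headed Exclusion Criteria is the formal statement of eligibility and it gives the other answer.

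A second reply is that the delay is short and that the protocol justifies it first on its own terms, comparing it with the doses that patients miss in everyday life. The cardiac exclusion is an added precaution. This stands too, and it lowers the importance of the point. A reader might infer that Section IV.D makes the safety of the delay depend on the angina exclusion. The text says only that the exclusion reduces risk further.

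A third reply is that *ongoing* may have been meant as another word for *unstable*. The documents define neither. If that was the intent, the *or* is redundant and the wording still needs correcting. For the same reason it is safer not to speak of stable angina, a term that the protocol does not use.

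The Stopping Criteria are not a separate fault. They concern new events and follow the list's narrower term, so they inherit the same discrepancy.

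**Conclusion.** The plan is wrong as written: it contradicts itself on a participant-safety exclusion. The conclusion rests on one reading, that *ongoing or unstable* is broader than *unstable* alone. It concerns patients with ongoing angina that is not unstable who take one of the two drug classes. Their number is unknown and may be zero. The point deserves correction because it affects who may be asked to delay a dose. It is not among the most serious, because the protocol rates the delay as minimal risk and the remedy is a change of wording.

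Two stronger readings are tempting, and the documents support neither.

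- *Heart failure.* A reader might infer the same gap, because Section IV.E says that "patients with ongoing heart failure or with GFR < 30 mL/min/1.73m² corresponding to chronic kidney disease stage 4 or 5 will be excluded" while the exclusion list uses a 6-month window. But Section IV.D and the list carry the same 6-month term, heart failure that is ongoing at enrollment is naturally present within the preceding 6 months, and the Stopping Criteria list congestive heart failure without a window. A gap appears only if the window is read as the date of onset, which the text does not say.
- *Primary aims.* A reader might infer that distorted DSI values enter the primary analysis. Section IV.E attributes possible changes in cholate clearance to heart failure and severe renal failure. No passage says that angina alters clearance or DSI. Primary Aims 1 and 2 are unaffected.

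**What to change.** Reconcile the angina wording in three places: the Exclusion Criteria and Stopping Criteria in Section IV.B, and the dose-delay paragraph in Section IV.D. All three should carry the same term, defined clearly enough that two people screening the same patient would agree.

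If the broader term is kept, it belongs in both lists. If the narrower term is kept, Section IV.D should no longer say that ongoing angina is excluded, and its account of the risk of the delay should be restated for the patients who can then enroll. The choice is a clinical one for the sponsor and the ethics committee, and this review takes no position on it.

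The cost is a short wording amendment. The statistical analysis does not change. Depending on the choice, some patients who pass the present list may become ineligible; the documents do not allow their number to be estimated. If enrollment has begun, the sponsor should also check whether any enrolled patient falls between the two wordings.

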Correlation and Comparison of the HepQuant® Disease
Severity Index (DSI) With Hepatic Venous Pressure
Gradient (HVPG)

NCT02523196

Protocol Version: August 11, 2015

Protocol #: 15-0520

Project Title: Correlation and comparison of the HepQuant® Disease Severity Index (DSI) with Hepatic Venous Pressure Gradient (HVPG)

Principal Investigator: [name].

Version Date: August 11th, 2015

I. Hypotheses and Specific Aims:

Hypothesis

The HepQuant® (HQ)-SHUNT test is an appropriate alternative to Hepatic Venous Pressure Gradient (HVPG) testing.

Specific Aims

HQ-SHUNT is safe, simple to administer, noninvasive, cost-effective, and well tolerated by patients. In order to prove that the HQ-SHUNT test is an appropriate alternative to measurement of HVPG we will conduct a head-to-head comparison of HQ-SHUNT to HVPG. In this study, 100 consecutive patients with various etiologies of liver disease who have undergone technically successful HVPG testing will subsequently undergo HQ-SHUNT testing.

Primary Aim 1: Create the ROC curve of the Disease Severity Index (DSI) from HQ-SHUNT for defining patients with (HVPG ≥ 6 mmHg) and without (HVPG < 6 mmHg) portal hypertension. From the ROC, define the optimal cutoff of DSI and the sensitivity, specificity, and positive and negative predictive values.

Primary Aim 2: In patients with portal hypertension (HVPG ≥ 6 mmHg), define the optimal relationship of DSI to HVPG.

Exploratory Aims

Approximately 90% of patients undergoing HVPG will have liver biopsy performed as part of the procedure. In addition, most of the patients undergoing HVPG will have undergone or will undergo upper gastrointestinal endoscopy (EGD) to evaluate for varices and variceal treatment. This allows a head-to-head comparison of DSI from HQ-SHUNT with HVPG in identifying patients with cirrhosis and patients with varices. Finally, we will also compare the tolerability of both HVPG and HQ-SHUNT, since tolerability of procedures is critical for patient acceptance and the ability to perform serial testing.

Exploratory Aim 1: Compare the cutoffs of DSI 16.5 and HVPG 6 mmHg in identifying patients with cirrhosis.

Exploratory Aim 2: Compare the cutoffs of DSI 20 and HVPG 10 mm Hg in identifying patients with varices.

Exploratory Aim 3: Survey patients on their experience of having both HQ-SHUNT and HVPG procedures.

II. Background and Significance:

The Clinical Problem in Liver Disease Assessment and Liver Disease Drug Development

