Drug companies are investing billions of dollars in developing new anti-fibrotic drugs to treat the ~30 million Americans with liver fibrosis/cirrhosis, but these efforts are hindered because the best method to quantify liver disease progression and the efficacy of new drugs is HVPG, which is invasive, painful, difficult to perform, and very expensive (~\$7000 - \$9000/test). In contrast, HQ-SHUNT is noninvasive, safe, relatively painless, easy to administer, cost-effective, and can outperform HVPG, and would have great value by allowing the rapid and accurate evaluation of new liver drugs and therapies. Drug companies have expressed interest and supported some small pilot studies of HQ-SHUNT but have asked how well this technology compares to HVPG. The proposed project has been approved for funding with a Colorado Bioscience Discovery and Evaluation Grant awarded to [name], and will be a proof-of-concept study to directly compare HQ-SHUNT testing to HVPG testing.

Monitoring Disease Progression in Chronic Liver Disease

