
the d4-Cholate dose / d4-Cholate AUC and the Portal HFR is the Oral Clearance normalized to patient weight (mL/min/kg). The concentration of d4-Cholate (μM) at 60 min was found in previous studies to exhibit a reasonable correlation ($r^2 = 0.88$) with Portal HFR so this single blood sample will also be evaluated as a simplified testing approach. The cholate shunt fraction is calculated as $100\% \times \text{Systemic HFR} / \text{Portal HFR}$. The DSI is calculated as $5.34 (\text{SHUNT}) - 6.65 (\text{Lne Portal HFR}) - 8.57 (\text{Lne Systemic HFR}) + 44.66$, and varies from ~ 0 in the healthiest liver to ~ 50 at liver failure.

SURVEY OF PATIENT TOLERABILITY

After undergoing both procedures, at the completion of the HQ-SHUNT test (always the last test), the patients would then be given two surveys, one for HVPG and another for HQ-SHUNT. The purpose of these surveys is to have the patient record their experiences with each procedure as regards their pain, discomfort, inconvenience, and willingness to undergo the procedures again. The two surveys are very similar but are nuanced for the type of testing.

D. Description, Risks and Justification of Procedures and Data Collection Tools:

Only patients who are already scheduled to have an HVPG procedure as part of their standard-of-care will be recruited to participate in this study. Most of these patients will also have liver biopsy either prior to or at the time of the HVPG procedure. In addition, these patients often undergo esophageal endoscopy procedures as part of their standard-of-care. While we will collect the data from these procedures, the subjects will not be exposed to any additional risks from these procedures beyond those associated with these standard-of-care procedures. Neither biopsy nor EGD are requirements for enrollment into this study of HVPG and HQ-SHUNT. The only additional risks will be those incurred from the HQ-SHUNT test.

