Primary Aim 1: Assuming that there are 50 patients with and 50 patients without portal hypertension in the study, a sample size of 50 from the portal hypertension group and 50 from the no portal hypertension group achieve 80% power to detect a difference of 0.14 between the area under the ROC curve (AUC) for DSI under the null hypothesis of 0.65 and an AUC under the alternative hypothesis of 0.79 using a two-sided z-test at a significance level of 0.05. The data are continuous responses. The AUC is computed between false positive rates of 0 and 1. The ratio of the standard deviation of the responses in the negative group to the standard deviation of the responses in the positive group is 1.

The following table shows the range of AUC's that can be detected based on alternative scenarios for the null hypothesis AUC using HQ-SHUNT:

Numeric Results for Testing AUC0 = AUC1 with Continuous Data

Test Type = Two-Sided. False positive rate1 = 0.000. False positive rate2 = 1.000. B (ratio of SDs) = 1.000.

Power	N+	N-	AUC0	AUC1	Difference	Alpha	Beta
0.80000	50	50	0.6500	0.7945	0.1445	0.05000	0.20000
0.80000	50	50	0.6600	0.8029	0.1429	0.05000	0.20000
0.80000	50	50	0.6700	0.8113	0.1413	0.05000	0.20000
0.80000	50	50	0.6800	0.8196	0.1396	0.05000	0.20000
0.80000	50	50	0.6900	0.8278	0.1378	0.05000	0.20000
0.80000	50	50	0.7000	0.8359	0.1359	0.05000	0.20000
0.80000	50	50	0.7100	0.8439	0.1339	0.05000	0.20000
0.80000	50	50	0.7200	0.8518	0.1318	0.05000	0.20000
0.80000	50	50	0.7300	0.8597	0.1297	0.05000	0.20000
0.80000	50	50	0.7400	0.8674	0.1274	0.05000	0.20000
0.80000	50	50	0.7500	0.8751	0.1251	0.05000	0.20000
0.80000	50	50	0.7600	0.8826	0.1226	0.05000	0.20000
0.80000	50	50	0.7700	0.8901	0.1201	0.05000	0.20000
0.80000	50	50	0.7800	0.8975	0.1175	0.05000	0.20000
0.80000	50	50	0.7900	0.9047	0.1147	0.05000	0.20000
0.80000	50	50	0.8000	0.9119	0.1119	0.05000	0.20000

Primary Aim 2: Assuming that there are 50 patients with portal hypertension, the following table shows the 95% confidence intervals around correlations ranging from 0.4 to 0.8 with a sample size of 50 patients with portal hypertension:

Numeric Results for Two-Sided Confidence Intervals for One Correlation

Confidence Level	Sample Size (N)	Actual Correlation	Width	Lower Limit	Upper Limit	Width if R = 0.0
0.950	50	0.473	0.400	0.137	0.610	0.557
0.950	50	0.426	0.500	0.257	0.683	0.557
0.950	50	0.367	0.600	0.386	0.753	0.557
0.950	50	0.295	0.700	0.524	0.819	0.557
0.950	50	0.211	0.800	0.671	0.882	0.557

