Correlation (R) is the assumed sample correlation.
Width if R = 0.0 is the maximum width for a confidence interval with sample size N.

For the linear regression analysis, a sample size of 50 achieves 80% power to detect a change in slope from 0 under the null hypothesis to 0.50 under the alternative hypothesis when the standard deviation of DSI is 3, the standard deviation of HVPG is 4.00, and the two-sided significance level is 0.05.

General Statistical Analysis

Primary Aim 1. It is expected that both HQ-SHUNT results and HVPG measurements will reflect the extent of liver disease. Higher pressures will in general be associated with lower Systemic HFR and Portal HFR, and with higher SHUNT and DSI. The performance of DSI to identify patients with portal hypertension (HVPG ≥ 6 mmHg) will be determined by ROC analysis. Optimal DSI cutoff, sensitivity, specificity, PPV, and NPV will be defined.

Primary Aim 2. We will develop models of the relationships of HQ-SHUNT test results to the HVPG test results based on correlations. We expect there to be a linear relationship for HVPG pressures between 6 and 25 mmHg (i.e. in patients with portal hypertension) and will assess the correlation (with 95% confidence intervals) for HVPG vs. DSI in the 50 patients expected to have HVPG pressures ≥ 6 mmHg. Linear regression will be used to assess the relationship between these variables, taking other covariates into account, and R^2 values will be reported.

Exploratory Aims:

Exploratory Aim 1. It is expected that both HQ-SHUNT results and HVPG measurements will, in general, reflect the extent of liver disease, as measured by the liver fibrosis stage and by the D'Amico cirrhosis stage. Regression models will be developed of the relationships of HQ-SHUNT test results to fibrosis stage and to cirrhosis stage. Likewise regression models will be developed of the relationship of HVPG portal pressure to fibrosis stage and to cirrhosis stage. It is expected that correlations will be found similar to those shown in Fig 3, but now demonstrated in the same patient population.

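### Primary Aim 1 chooses the DSI cutoff and reports its accuracy in the same patients, with no interval and no correction; an accuracy-maximising cutoff makes those figures too high on average

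*Combined protocol and SAP*

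**What the plan says.** Three places in the combined protocol and SAP describe the output of Primary Aim 1, all in the same way.

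- Section I, Primary Aim 1: "From the ROC, define the optimal cutoff of DSI and the sensitivity, specificity, and positive and negative predictive values".
- Section IV.A, Primary Aim 1: the "DSI cutoff for portal hypertension will be defined from ROC analysis".
- Section IV.F, General Statistical Analysis, Primary Aim 1: "Optimal DSI cutoff, sensitivity, specificity, PPV, and NPV will be defined".

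The patients are "100 consecutive patients with various etiologies of liver disease who have undergone technically successful HVPG testing" (Section I), so the split by HVPG is not controlled. The even split is a planning premise: "Assuming that there are 50 patients with and 50 patients without portal hypertension in the study" (Section IV.F, Power and Sample size). The sample size rests on the AUC alone, with "80% power to detect a difference of 0.14 between the area under the ROC curve (AUC) for DSI".

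Section IV.F plans 95% intervals for the Primary Aim 2 correlation. It names the Youden index for Exploratory Aim 2. It carries neither over to Primary Aim 1. The DSI itself is not refitted: the formula introduced by "The DSI is calculated as" in Section IV.C has fixed coefficients.

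**The concern.** A cutoff picked because it performs best in a sample benefits from the chance pattern of that sample. Scoring it in the same patients counts that luck as accuracy. With 50 or fewer patients per group the effect can be several percentage points, and it favours the test under study.

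The four figures are a stated output of a primary aim. They would be read as support for the Section I hypothesis that HQ-SHUNT can stand in for HVPG testing. Under the plan as written, a reader would have neither an interval to judge their precision nor any sign that they are apparent values.

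**Working it through.** **Inputs from the plan (Section IV.F).** 50 patients with and 50 without portal hypertension; AUC 0.65 under the null and 0.79 under the alternative (table row 0.7945); SD ratio 1; two-sided alpha 0.05; power 80%.

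**Assumptions added here.** DSI normally distributed in each group; the cutoff criterion; the unequal splits.

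**Step 1: the plan's own figure.** Large-sample Hanley-McNeil variance: V(A) = (Q1 + Q2 − 2A²)/50, with Q1 = A/(2 − A) and Q2 = 2A²/(1 + A).

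- A = 0.65: (0.4815 + 0.5121 − 0.8450)/50 = 0.00297, SE 0.0545.
- A = 0.7945: (0.6591 + 0.7035 − 1.2625)/50 = 0.00200, SE 0.0447.
- Power = Φ((0.1445 − 1.96 × 0.0545)/0.0447) = Φ(0.84) = 80.0%.

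The stated power is reproduced.

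**Step 2: accuracy available in the population.** With equal SDs the groups lie d = √2 × z(AUC) apart. For AUC 0.7945, d = 1.163. The best cutoff is the midpoint, where sensitivity = specificity = Φ(d/2) = 71.9% and J = 0.439.

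**Step 3: apparent against true accuracy.** Each simulated trial draws DSI from N(d, 1) and N(0, 1) and picks cutoff c in the sample. Apparent values are the observed proportions at c. True values at the same c are sensitivity 1 − Φ(c − d) and specificity Φ(c), with PPV and NPV following at that split. Bias is the mean of apparent minus true.

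Youden at 50/50, AUC 0.7945 (20,000 trials), for sensitivity, specificity, PPV and NPV:

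- Apparent: 76.8, 73.1, 75.1, 77.1%.
- True: 72.8, 69.1, 71.2, 72.8%.
- Difference: 4.0, 4.0, 3.9, 4.3 points. J is 0.499 apparent against 0.419 true.

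Bias in points by criterion and split (with/without portal hypertension), AUC 0.79, 10,000 trials per row; the last row uses AUC 0.7945 and 20,000 trials:

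| Criterion | Split | Sens. | Spec. | PPV | NPV |
|---|---|---|---|---|---|
| Youden | 50/50 | +4.0 | +4.1 | +4.0 | +4.3 |
| Youden | 60/40 | +3.4 | +5.1 | +3.7 | +4.7 |
| Youden | 70/30 | +2.8 | +6.5 | +3.3 | +5.2 |
| Youden | 30/70 | +6.4 | +2.8 | +5.1 | +3.3 |
| Closest to corner | 50/50 | +3.0 | +3.0 | +2.9 | +2.9 |
| Closest to corner | 70/30 | +2.1 | +4.7 | +2.3 | +3.6 |
| Sensitivity at least 90% | 50/50 | +2.0 | +1.3 | +1.2 | +1.9 |
| Sensitivity = specificity | 50/50 | +0.3 | +0.2 | 0.0 | +0.1 |

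In the 90% row, specificity bias falls to 0 if the cut is placed on an observed value. Under Youden at 50/50 each measure is too high in 76 to 83% of trials, and all four together in 57%. With SD ratios from 0.67 to 2.0 the Youden bias at 50/50 stays between 3.0 and 4.5 points.

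**Step 4: scale.** The 95% half-width for 72% is 1.96 × √(0.72 × 0.28/n): 12.4 points at n = 50 and 16.1 at n = 30. As an example, 36/50 has a Wilson interval of 58.3 to 82.5%.

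**Step 5: the AUC.** In the simulations the mean estimated AUC stayed within about 0.001 of the true value. It uses no cutoff, and the DSI formula is fixed.

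**The case against.** **Aim 1 names no criterion.** This stands and limits the point. A reader might infer that the figures are inflated however the cutoff is chosen. The documents do not support that: a cutoff that only equates sensitivity and specificity gives bias of 0 to 0.3 points. The upward direction is conditional on a criterion that maximises accuracy in the sample. That is the natural sense of an optimal cutoff, and it fits the one criterion the protocol names elsewhere, but it remains an assumption for Aim 1.

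**The consequence is limited.** This stands too. Section II says the project "will be a proof-of-concept study to directly compare HQ-SHUNT testing to HVPG testing", the powered quantity is the AUC, and no decision threshold depends on the four figures. A reader might also infer that the case in Section IV.G for replacing HVPG rests on them. It does not: that sentence rests on correlation between the two tests, which is the subject of Primary Aim 2 and has planned intervals.

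**The bias is smaller than the sampling error.** True, so the missing intervals are the larger gap. But the bias has a direction, and sampling error in a single study may go either way.

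**The remedy is imperfect.** Correction leaves some bias. A Wilson interval at the corrected value covers the true accuracy at the cutoff this sample picked (about 96% at 50/50), but accuracy at the population-optimal cutoff only about 70 to 74% of the time. The target must therefore be stated. This is no reason to report uncorrected values without intervals.

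**Conclusion.** The point holds in conditional form. Primary Aim 1 plans apparent accuracy figures with no interval and no correction for selection. If the cutoff maximises accuracy in the sample, they are too high on average: about 4 points each with Youden at 50/50, about 3 with closest-to-corner, and about 6 for the measure estimated in the smaller group at 70/30 or 30/70. These sizes rest on normal DSI, AUC 0.79 and equal SDs.

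The AUC and its power calculation are not affected by cutoff selection. A reader might go further and call the AUC unbiased in every respect. The check does not show that: Section IV.C limits HQ-SHUNT testing to stable patients and censors those who decompensate between the two tests, and any effect of this on the AUC was not examined.

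The matter should be put right before the analysis. What is at stake is how precisely and how candidly a primary-aim output is reported.

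**What to change.** Add to the Primary Aim 1 text in Section IV.F:

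1. **Criterion.** Name it in advance, for example the Youden index as in Exploratory Aim 2.
2. **Correction.** Correct sensitivity and specificity by bootstrap optimism correction. Resample separately within patients with and without HVPG ≥ 6 mmHg and re-select the cutoff in each resample. Subtract the mean of (value in the resample minus value of that cutoff in the study data). Derive PPV and NPV from the corrected pair at the observed prevalence p, for example PPV = sens × p / (sens × p + (1 − spec)(1 − p)). Show the uncorrected values alongside, labelled as apparent.
3. **Intervals.** Give 95% Wilson intervals at the corrected sensitivity and specificity, and a DeLong interval for the AUC. State that the Wilson intervals cover true accuracy at the cutoff chosen in this sample, not at the population-optimal cutoff. For PPV and NPV, state the interval method and denominator.
4. **Status.** Call the cutoff provisional until it is validated externally.

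**Cost.** A few lines of text and a short program; no new patients or data. With Youden, reported accuracy falls on average by about 3 points per measure at 50/50, and by about 4 points for the measure in the smaller group at 70/30 or 30/70. About 1 to 2.5 points of bias remain, most in the smaller group. The gain in precision is modest: at 50/50 the root mean square error falls from 6.8 to 6.1 points for sensitivity and from 7.2 to 6.4 for specificity. Repeated 10-fold cross-validation brings the bias within 0.8 point, but its error is larger than with no correction (7.7 against 6.8 points for sensitivity, 8.2 against 7.3 for specificity).
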